9.3 Exploratory Analyses

ALL Treatment Group:

TSQM domain scores at Visit 1, Visit 2, Visit 3, Visit 4 and Visit 5 will be summarized and presented descriptively for non-naïve patients. There are three domains which include effectiveness (3 items), convenience (3 items) and global satisfaction (3 items).

TSQM domain change from baseline (Visit 1) scores at Visit 2, Visit 3, Visit 4 and Visit 5 will be summarized and presented descriptively for non-naïve patients using 2 different approaches, LOCF and no LOCF. Change from baseline scores will be analysed using a two-sided paired t-test or a non-parametric equivalent if warranted by the data.

TSQM domain scores at Visit 2, Visit 3, Visit 4 and Visit 5 will be summarized and presented descriptively for naïve patients. There are three domains which include effectiveness (3 items), convenience (3 items) and global satisfaction (3 items).

TSQM domain change from baseline (Visit 2) scores at Visit 3, Visit 4 and Visit 5 will be summarized and presented descriptively for naïve patients using 2 different approaches, LOCF and no LOCF. Change from baseline scores will be analysed using a two-sided paired t-test or a non-parametric equivalent if warranted by the data.

10.0 SAFETY ANALYSES

The following safety analyses will be performed using the Safety population.

10.1 Adverse Events

Adverse event data will be tabulated separately for each treatment group (ALL, BID, TID) by system organ class and preferred term. Adverse events will be summarized by presenting counts and percentage of patients (each patient contributes a single count to a category) and the total number of events in each system organ class and in each system organ class/preferred term.

In addition, adverse event data with a possible drug relationship (possible, probable, definitely related) will be tabulated separately for each treatment group (ALL, BID, TID) by system organ class and preferred term. Adverse events will be summarized in a similar manner as above.

As well, adverse event data will be tabulated separately for each treatment group (ALL, BID, TID) by system organ class, preferred term and severity (mild, moderate, severe). Adverse events will be summarized by presenting counts and percentage of patients (each patient contributes a single count to a category) and the total number of events in each system organ class by severity and in each system organ class/preferred term by severity.

The Medical Dictionary for Regulatory Activities (MedDRA™ version 20.1) will be utilized for the coding of adverse events.

All adverse events that occurred on or after the date of informed consent up to 30 days after the end of study date will be summarized.

Serious adverse events will not be tabulated due to the expected small number of events. Narratives will be provided for serious adverse events.

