3.0 STUDY OVERVIEW

This is a phase 4, multi-centre study consisting of two study periods and a post study follow-up.

90-Day Treatment Period: With potential extension by 30 days for those patients requiring a dose increase, as determined by the treating physician. Participants receiving 122.5mg of Natesto™ (5.5 mg of testosterone) per nostril twice daily may have an increased daily dose adjustment on Day 90, based on their hypogonadism symptoms.

1-Day Study Completion Period: Patient will return to the site for examination, discussion of symptoms with physician and questionnaire completion. Serum testosterone levels will be determined for all patients on Day 90 (BID dose) and on Day 120 for the TID patients.

Post Study Follow-Up: All study patients will be followed up at Day 150 after the Treatment Phase to determine if they have continued using NATESTO and why (or why not?).

Schedule of Procedures

Study Phase	Treatment Period						
	Treatment Start	Efficacy Analysis				Post Study Follow Up	Early Withdrawal/Termination
	Day 0	Day 30 +/- 3 days	Day 60 +/- 3 days	End of Study: BID Patients Day 90 +/- 3 days	End of Study: TID Patients Day 120 +/- 3 days	Day 150 +/- 3 days	
Visit	1	2	3	4 ^a	5 ^b	6	
Location/Type	clinic	telephone	telephone	clinic	clinic	telephone	clinic
Study Procedures:							
Inclusion/exclusion criteria	X						
Informed consent	X						
Medical history	X			X	X		
Demographics	X						
Physical examination + nasal exam	X			X	X		X
Height and weight	X			X	X		X
Vital signs (HR, BP, RR, and temperature)	X			X	X		X
Serum total testosterone plus safety labs	X ^c			X	X ^d		X
Participant training on NATESTO administration	X						
Provide Study Drug Access Card for NATESTO	X						
Provide Pharmacy Prescription	X			X ^g			
Potential study drug daily dose increase to TID				X			
TSQM	X ^e	X	X	X	X		X
qADAM	X ^f	X	X	X	X		X
Patient Preference + Use	X			X	X		X
Concomitant medications	X	X	X	X	X		X
Assess adverse events	X	X	X	X	X		X
Assess voluntary treatment continuation						X	

- a. All patients are required to complete Visit 4
- b. Only patients assigned to NATESTO TID are required to complete Visit 5
- c. Naïve patients will require confirmation of hypogonadism by serum testosterone within the last 6 months
- d. Only patients who continued on TID
- e. TSQM to be completed by non-naïve patients only
- f. qADAM to be completed by all patients

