- g. Patients who are assigned to NATESTO TID will be provided with a new Pharmacy Prescription increasing their dosage to TID

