7.0 DATA CONVENTIONS

7.1 Definitions

Visit 1 (Day 0) is defined as the day in which the patient provides informed consent and starts the study. All study days are determined relative to Visit 1 (Day 0).

End of treatment is defined as the day on which the last dose of treatment is taken. This date was not collected for this study.

End of study is defined as the last day on which data were collected from the patient. Using the Early Termination Visit eCRF, it is the date of early termination. Using the Visit 6 - Post Study Follow-Up (Day 150) eCRF, it is the post study follow-up date. Otherwise, it is the date of last contact, if the patient was lost to follow-up, or the date of death, if the patient died.

Baseline serum testosterone values will be defined as those values recorded on Visit 1 (Day 0). Naive patients were asked for 2 measurements (average used in analysis) and non-naive patients were asked for 1 measurement at Baseline (Visit 1/Day 0).

Serum Testosterone will be reported in (nmol/L). If value is reported in (ng/dL) then value will be multiplied by 0.0347 to convert to (nmol/L).

Testosterone collected in (pmol/L) will be considered Free Testosterone and will not be used in any analyses.

Hematocrit will be reported in (%). Values will be multiplied by 1 and if the value is less than 1 then the value will be multiplied by 100.

Total Cholesterol will be reported in (mmol/L). If value is reported in (mg/dL) then value will be divided by 38.67 to convert to (mmol/L).

LDL will be reported in (mmol/L). If value is reported in (mg/dL) then value will be divided by 38.67 to convert to (mmol/L).

HDL will be reported in (mmol/L). If value is reported in (mg/dL) then value will be divided by 38.67 to convert to (mmol/L).

Triglycerides will be reported in (mmol/L). If value is reported in (mg/dL) then value will be divided by 88.57 to convert to (mmol/L).

Hemoglobin will be reported in (g/L). If value is reported in (g/dL) then value will be divided by 0.1 to convert to (g/L).

ALT and AST will be reported in (U/L).

Study duration (days) will be defined as the (end of study date – date of informed consent + 1).

The ALL treatment group will be defined as patients who were either naïve or non-naïve.

The BID treatment group will be defined as patients who were either naïve or non-naïve and did not titrate to TID (Visit 5/Day 120).

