The TID treatment group will be defined as patients who were either naïve or non-naïve and did titrate up to TID (Visit 5/Day 120).

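### Adverse events are tabulated by whether the patient ever titrated, so about 90 days of BID-period events in titrated patients are reported under TID and are absent from BID

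*SAP*

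**What the plan says.** Section 10.1 fixes the columns: "Adverse event data will be tabulated separately for each treatment group (ALL, BID, TID) by system organ class and preferred term". Drug-related events and events by severity use the same columns. The statistics are "counts and percentage of patients (each patient contributes a single count to a category) and the total number of events". Events count from the consent date until 30 days after the end-of-study date. Section 7.1 sets that date at the Day 150 follow-up contact for patients who have one.

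Section 7.1 makes the column labels properties of the whole patient. The TID group is defined by the condition "and did titrate up to TID (Visit 5/Day 120" and the BID group by "did not titrate to TID (Visit 5/Day 120". Neither definition refers to the dose at the time of an event.

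Section 3.0 places the change of dose late. Patients on the twice-daily regimen "may have an increased daily dose adjustment on Day 90", with a potential 30-day extension. Footnote g to the schedule says that patients assigned to TID "will be provided with a new Pharmacy Prescription increasing their dosage to TID", and the schedule marks this at Visit 4. Footnote b adds: "Only patients assigned to NATESTO TID are required to complete Visit 5". In the schedule, adverse event assessment is marked at Visits 1 to 5 and at Early Termination, but not at the Day 150 telephone contact.

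The SAP has no dose-at-onset rule, no split of a titrated patient's events before and after titration, and no exposure denominator.

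**The concern.** Columns headed BID and TID in an adverse event table invite reading by dose, and dosing frequency and safety monitoring are both secondary objectives (section 2.2). On the SAP's own definitions that reading fails. Every titrated patient has spent about three months on BID, and whatever happened in that time is moved to TID. The BID column loses the same events. It also holds everyone who left before Visit 4, because such a patient had no opportunity to titrate.

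The laboratory, testosterone and vital-sign summaries are less exposed, because they are reported by visit: in titrated patients, Visit 4 values precede the increase and Visit 5 values follow it. The adverse event tables have no time dimension, so a reader cannot recover the dose from them. At stake is whether the study report describes events on each regimen correctly.

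**Working it through.** The SAP gives no adverse event rate or count, so there is no planned figure to reproduce. The inputs from the SAP are:

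- titration at Visit 4, Day 90 ± 3 (sections 3.0 and 7.2);
- end of the TID period at Visit 5, Day 120 ± 3 (same sections);
- end of study at the Day 150 contact, plus 30 days of event counting (sections 7.1 and 10.1).

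**Share of a titrated patient's treatment days spent on BID** = Visit 4 day / Visit 5 day.

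- Nominal: 90/120 = 75.0%.
- Lowest within the windows: 87/123 = 70.7%.
- Highest within the windows: 93/117 = 79.5%.

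**Length of the TID period** = Visit 5 day − Visit 4 day. Nominal: 120 − 90 = 30 days. Range: 117 − 93 = 24 to 123 − 87 = 36 days.

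**Counting window.** Day 150 + 30 = Day 180. After the last treatment visit, 180 − 90 = 90 days remain for a BID patient and 180 − 120 = 60 days for a TID patient.

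**Effect on event totals.** Let R be the ratio of the daily event rate on TID to that on BID. R is an assumption, as are constant rates and no early withdrawals. Events per TID-group patient relative to a BID-group patient are:

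- Capture A, stopping at the last treatment visit (Visit 4 for BID, Visit 5 for TID): (90 + 30R)/90.
- Capture B, to Day 180 with each patient continuing on the same dose: (90 + 90R)/180.

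| R | Capture A | Capture B |
|---|---|---|
| 1 | 120/90 = 1.33 | 180/180 = 1.00 |
| 2 | 150/90 = 1.67 | 270/180 = 1.50 |
| 3 | 180/90 = 2.00 | 360/180 = 2.00 |

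Under A, setting (90 + 30R)/90 = R gives R = 1.5. Below that the table shows more than the true ratio, and above it less. Under B the ratio is (1 + R)/2, which equals R at R = 1 and is smaller than R for any R above 1, so a TID excess can only be diluted.

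**Effect on patient percentages.** These move less than event totals. Take equal rates on both doses (R = 1), Capture A, and an assumed 30-day risk p. The percentage with at least one event is 1 − (1 − p)³ over 90 days and 1 − (1 − p)⁴ over 120 days.

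| p | BID column | TID column | Ratio |
|---|---|---|---|
| 5% | 14.3% | 18.5% | 1.30 |
| 10% | 27.1% | 34.4% | 1.27 |
| 20% | 48.8% | 59.0% | 1.21 |

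The risk in the 30 days actually on TID would be p itself: 5%, 10% or 20%.

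**The case against.** The SAP never promises safety by dose. The objective is safety monitoring, no comparison of BID with TID is planned, and BID and TID serve as cohort labels elsewhere: section 5.2 reports Visit 1 preference for TID patients, before anyone takes TID. Read with section 7.1 in hand, the columns are consistent with the rest of the plan. Section 8.0 also leaves presentation to a Table Mock-Up that is not shown and could carry a footnote or a split. Finally, the study is descriptive, with about 100 patients, so a rebuilt safety analysis would be out of proportion.

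Most of this limits the harm without removing the defect. Consistent labels do not tell the reader of an adverse event table that most of the treatment time under TID was BID time. The Table Mock-Up may help, but the columns, their definitions and the counting window are set in the SAP, which contains no rule for a split. The proportionality argument stands and keeps the remedy small.

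A reader might go further and infer that the planned tables will show a spurious excess of events on TID. The documents do not support that. The excess at R = 1 appears only if capture stops at the last treatment visit. The absence of a scheduled assessment at Day 150 makes that possible. However, section 10.1 counts to the same nominal Day 180 for both groups, and the Day 150 contact is meant "to determine if they have continued using NATESTO and why (or why not", so some patients may still be dosing. With full capture and continued dosing the ratio at R = 1 is 1.00.

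**Conclusion.** The concern holds as a problem of attribution. As written, the SAP reports a titrated patient's BID-period events under TID and removes them from BID; nominally 75% (70.7% to 79.5%) of the treatment days behind the TID column are BID dosing. This part rests only on the SAP's definitions and visit days. The BID and TID columns cannot be read as safety by dose.

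The direction and size of any distortion in the counts cannot be fixed from the SAP. They depend on R, on how far events are captured after the last treatment visit, and on early withdrawals; the ratios above are illustrations. Nor do the documents support calling the overall safety results wrong: the ALL column is unaffected and no BID-versus-TID test is planned. Severity is minor to moderate. Confidence is medium, because the Table Mock-Up was not available.

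**What to change.** Keep the ALL table and the counting window, and tabulate events by dose period at onset, split at the Visit 4 date:

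- **BID period:** all Safety patients, from Day 0 to Visit 4 or Early Termination.
- **TID period:** titrated patients, from Visit 4 to Visit 5 or Early Termination.
- For each period, give the number of patients at risk and person-time from visit dates.
- List events with onset after the last treatment visit separately, because section 7.1 says the last-dose date was not collected.

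If the titration-status columns are kept, footnote that TID includes pre-titration events; this is the minimum change. In either case, state that the TID period covers only patients who reached Day 90 and were selected on symptoms, so a difference between periods is not a dose effect.

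The cost is some SAP wording and a few derivations from visit and event-onset dates. The downside is that visit dates only approximate the dose switch and the end of exposure, and that the TID period is short (24 to 36 days), so its estimates will be imprecise.

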6.5 Safety Population

The Safety population includes all patients who received at least one dose of the study drug. All safety data including adverse events, physical examination parameters, vital signs, total testosterone and laboratory data will be analysed using the Safety population.

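### Adverse-event tables count from informed consent with no treatment-emergent cut, so events before the first dose can appear as Natesto experience; the effect is probably small

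*SAP*

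**What the plan says.** Section 10.1 sets the counting window: "All adverse events that occurred on or after the date of informed consent", until 30 days past the end of study. On grouping it says "Adverse event data will be tabulated separately for each treatment group (ALL, BID, TID) by system organ class and preferred term". The severity table uses the same grouping, as does a further table limited to events judged possibly, probably or definitely related.

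Section 6.5 defines who is counted: "The Safety population includes all patients who received at least one dose of the study drug".

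Section 7.1 fixes the time origin: "Visit 1 (Day 0) is defined as the day in which the patient provides informed consent and starts the study". It also makes BID and TID labels for the whole patient, according to whether he titrated to TID. It says that the date of last dose was not collected, and it defines no date of first dose.

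In the Section 3.0 schedule, the Day 0 column is headed "Treatment Start". That visit includes informed consent, training in administration, "Provide Study Drug Access Card for NATESTO", "Provide Pharmacy Prescription" and an assessment of adverse events. No row shows dispensing or a first dose at the site.

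**The concern.** Exposure decides which patients are counted but not which events. A patient enters the safety tables by taking at least one dose. Once he is in, every event since consent is counted under his BID or TID label, including any with onset before that dose. The SAP contains no definition of a treatment-emergent event and no separate display of pre-dose events.

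This matters more here than in a trial that doses in the clinic. The Day 0 visit provides a card and a prescription, which points to a pharmacy step between consent and first dose. Adverse events are also assessed at Day 0 itself, so a record can exist before any drug is taken. At stake is what the all-cause and severity percentages describe: experience on Natesto, or experience since consent.

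**Working it through.** The SAP gives no figure on this point, so there is none to reproduce. The check is a reading of the rules together, then arithmetic on the counting window.

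**Can a pre-dose event reach the tables?**
1. The window opens on the date of consent (Section 10.1), which is Day 0 (Section 7.1).
2. Adverse events are assessed at Day 0 (Section 3.0 schedule), so an event on that day can be recorded.
3. The Safety population removes patients who were never dosed (Section 6.5). It does not remove the pre-dose events of patients dosed later.
4. BID and TID are whole-patient labels (Section 7.1), so such an event falls in that patient's column.
5. No later rule takes it out of the all-cause or severity table. The related-events table would usually leave it out, because the investigator must judge it at least possibly related.

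The answer is yes.

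**How much of the window could be pre-dose?**

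Inputs:
- End of study for a completer is the post-study follow-up, nominally Day 150 (Sections 3.0 and 7.1).
- The window closes 30 days later (Section 10.1).
- The gap from consent to first dose, *g*, is not in the SAP. Values of 0, 1, 3, 7 and 14 days are assumed.

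Window: Day 0 to Day 150 + 30 = Day 180, which is 181 days counting both ends. It is the same for BID and TID completers.

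Share of the window before first dose = *g* / 181:

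| Assumed gap (days) | Calculation | Share |
|---|---|---|
| 0 | 0/181 | 0% |
| 1 | 1/181 | 0.6% |
| 3 | 3/181 | 1.7% |
| 7 | 7/181 | 3.9% |
| 14 | 14/181 | 7.7% |

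These are shares of counted time. They equal shares of events only if events are reported at a constant rate over the window. For a patient who terminates early the window is shorter, so the same gap is a larger share.

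**The case against.** The strongest reply is that the schedule itself places the start of treatment at Day 0, so the planned gap is zero. Consent and prescription fall at the same visit, with no screening period between them, and filling the prescription that day fits the text. This stands as a limit on size. It does not remove the rule's effect, since even on Day 0 an event before the first dose is counted.

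A second reply is that counting from consent is explicit, over-counts rather than under-counts, and contradicts nothing else in the SAP. An all-cause table makes no claim about causation, the related-events table deals with attribution, serious events get narratives, and there is no comparator arm to bias. Most of this is fair. What remains is that the all-cause and severity tables carry BID and TID headings with nothing to tell the reader that pre-dose events are included.

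Three stronger readings are tempting but not supported:
- *The drug is always obtained after Day 0.* This is an inference from the card and prescription rows. The SAP gives no dispensing date, first-dose date or delay.
- *Events on a prior testosterone product are credited to Natesto in non-naïve patients.* The SAP does not say what these patients take between consent and first dose, so this is speculation.
- *Pre-dose time is up to 16% or 12% of follow-up.* Those figures come from 14/90 and 14/120, which divide by the treatment period. The rule at issue is the counting window, and 14/181 gives 7.7%.

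**Conclusion.** The point holds as a minor one. Section 10.1 allows pre-dose events to be tabulated as BID or TID experience, because the population is conditioned on a dose and the events are not. The effect is probably small: nothing if dosing begins at consent, and at most 7.7% of a completer's nominal window over the assumed range of gaps up to 14 days. That range is an assumption, and the 181 days apply to a patient followed to Day 150. The SAP does not show that any pre-dose event occurred or that any delay was typical, so this is a matter of definition and labelling and not evidence that the safety results are distorted.

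**What to change.** Define a treatment-emergent event in Section 10.1 as one with onset or worsening on or after the first dose. Restrict the all-cause, related and severity tables to these events, and list earlier events separately so that none is lost. If the first-dose date was not recorded but the first pharmacy fill date was, use the fill date as a stated proxy.

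The SAP mentions neither date, so a fallback is needed. If neither exists, show events with onset on Day 0 in their own row and title the tables as events since consent. This fallback is rough: it sets apart any Day 0 event that followed a dose, and it misses pre-dose events from Day 1 onward.

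The cost is one definition, a date filter and revised table titles. The downside is that patients with no usable date keep all their events as treatment-emergent, so the separation will be incomplete; the number of such patients should be reported.

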2.2 Secondary Objectives

The secondary objectives of this study are to evaluate the following:

1. Improvement in hypogonadism symptoms
2. Patient treatment preference versus prior testosterone replacement therapy
3. Frequency of daily dose of Natesto™
4. Safety monitoring

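### SAP section 10.1 rules out tabulating serious adverse events because few are expected, so no planned table gives the proportion of patients with a serious event

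*SAP*

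**What the plan says.** Safety is among the secondary objectives (section 2.2, "Safety monitoring"), and adverse events are the first safety endpoint in section 5.3. Section 10.1 then plans three tables:

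- **All events:** "Adverse event data will be tabulated separately for each treatment group (ALL, BID, TID) by system organ class and preferred term".
- **Related events:** "adverse event data with a possible drug relationship (possible, probable, definitely related) will be tabulated separately for each treatment group".
- **Severity:** a further table "by system organ class, preferred term and severity (mild, moderate, severe").

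The statistics are fixed as well: "Adverse events will be summarized by presenting counts and percentage of patients (each patient contributes a single count to a category"), together with event totals. The scope is broad: "All adverse events that occurred on or after the date of informed consent up to 30 days after the end of study date will be" part of these summaries.

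Serious events are treated differently. The section says "Serious adverse events will not be tabulated due to the expected small number of events", followed by "Narratives will be provided for serious adverse events". Sections 6.5 and 10.0 make the Safety population (at least one dose) the basis of all safety analyses. Section 8.0 refers to an accompanying Table Mock-Up document for the details of presentation and sends data without a table to listings.

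**The concern.** The decision not to tabulate is made in advance and rests only on an expectation that numbers will be small. A small count is a reason for a short table. It is not a reason for no table, because a reader who wants to know how often serious events occurred needs the count set against its denominator.

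The wording also leaves a doubt about the other tables. The sentence that all adverse events are summarized is followed directly by one saying that serious events are not tabulated. The natural reading is that there is no separate serious-event table, but a programmer could take it to mean that serious events are left out of the general tables. That second reading would lower the reported adverse-event percentages.

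At stake is whether the report states, for a marketed product in a phase 4 study, what fraction of treated patients had a serious event, overall and by dosing group. No efficacy result depends on it.

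**Working it through.** The SAP gives no expected number or rate of serious events, so there is no figure of its own to reproduce. The check has two parts.

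**1. Can the serious-event incidence be read from the planned tables?**

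| Planned output (section 10.1) | Groups | Split by | Marks seriousness? |
|---|---|---|---|
| All events | ALL, BID, TID | system organ class, preferred term | No |
| Related events | ALL, BID, TID | the same, relationship at least possible | No |
| By severity | ALL, BID, TID | the same, by mild, moderate, severe | No |
| Serious events | none | narratives only | Yes, but not a table |

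A patient with a serious event adds one to a row of the first table exactly as a patient with a non-serious event does. The severity table does not separate them either: a serious event may be graded moderate, and a severe event may be non-serious. No combination of the three tables yields n/N for serious events. The Table Mock-Up, which is not available here, cannot be assumed to fill the gap, because a serious-event table there would contradict section 10.1. The stated fallback is listings, which, like narratives, leave the percentage to be worked out.

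**2. Is a table with few or no events uninformative?**

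Input: about 100 participants (section 4.0). Assumptions: all 100 are dosed, with 75 and 50 as a sensitivity range. The SAP gives no expected BID/TID split, so no subgroup sizes are used.

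For zero events the exact two-sided 95% upper limit is 1 − 0.025^(1/N):

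- N = 100: 1 − 0.025^(1/100) = 3.62%
- N = 75: 1 − 0.025^(1/75) = 4.80%
- N = 50: 1 − 0.025^(1/50) = 7.11%

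For x patients with an event, the exact (Clopper-Pearson) limits are the 0.025 quantile of Beta(x, N − x + 1) and the 0.975 quantile of Beta(x + 1, N − x). At N = 100:

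| x | % | Exact 95% CI |
|---|---|---|
| 2 | 2.0 | 0.24 to 7.04 |
| 3 | 3.0 | 0.62 to 8.52 |
| 5 | 5.0 | 1.64 to 11.28 |

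The chance of at least one patient with a serious event among 100 is 1 − (1 − p)^100:

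- p = 0.5%: 39%
- p = 1%: 63%
- p = 2%: 87%

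These values of p are assumed. They show that a serious-event row would not be empty by default, and the zero-event limits show that it would be worth printing if it were.

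**The case against.** The strongest reply is that little information is lost. The denominator is defined. Section 10.1 does not carve serious events out of its statement that all adverse events are summarized, so on the natural reading they count in the general tables, with percentages. Narratives are promised for serious events, so a reader can count the patients concerned, divide by the Safety population and, if there are none, apply the zero-event formula. The confidence limits above measure the imprecision of a small sample and are the same with or without a table. Section 1.0 also allows documented deviations where the data warrant them, so an unexpectedly high count could still be tabulated.

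All of this stands, and it limits the point to one of presentation. It does not justify the sentence: a hand count from narratives is a poor substitute for a row that the existing program can produce, and the reason given does not support leaving it out.

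A reader might go further and infer that serious events have no denominator or drop out of the safety tables altogether. The text does not say so. A reader might also infer that events leading to withdrawal will go unreported, since none of the three tables isolates them. That rests on silence alone: section 6.1 plans a report of patient disposition, section 8.0 leaves presentation to the Table Mock-Up, and neither output is available here. The SAP does not show that such a summary is missing.

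**Conclusion.** The point holds in a limited form. Section 10.1 expressly excludes serious adverse events from tabulation on a ground that does not support the exclusion, and its three tables do not separate them. The planned tables therefore give no incidence of patients with a serious event for ALL, BID or TID. The missing item is one row per group. It can be recovered by hand from the narratives and the Safety population count.

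This is a minor weakness in safety reporting in a single-arm, open-label study of about 100 patients. It has no bearing on the satisfaction or symptom-score analyses. The conclusion rests on the wording of section 10.1 and does not depend on the assumed sample sizes or event rates, which serve only to show that a small or zero count is worth reporting.

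**What to change.** Replace the sentence in section 10.1 that excludes serious events with text to this effect:

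> The number and percentage of Safety-population patients with at least one serious adverse event, and the number of such events, will be tabulated for the ALL, BID and TID groups, and shown even if zero. Serious events are also included in the all-event, related-event and severity tables. Narratives will be provided for all serious events.

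An exact 95% confidence interval for the overall percentage is optional. The second sentence removes the doubt about whether serious events stay in the general tables.

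The cost is a short change to the SAP, the matching entry in the Table Mock-Up, and one short table from the existing adverse-event program. No additional analysis method is needed.
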